6.2 Medical History

Medical history relevant to the ICU admission for each patient will be obtained during Screening. Past and present conditions, as well as surgical procedures, will be recorded for the main body systems. Medication history will include all medications taken and/or prescribed during the 7-day window prior to informed consent and those relevant to ICU admission..

6.3 Physical Examination

Physical examinations will be obtained at the Screening and End of Treatment. Any new condition or worsening of a pre-existing condition from Screening will be noted and recorded on the AE eCRF page.

An attempt should be made to perform a final physical examination on patients who complete Screening and enroll, but who discontinue from the study early, particularly if the patient is discontinuing from the study because of an AE.

6.4 Vital Signs

Vital signs will include measurements of blood pressure, respiratory rate, temperature, and pulse rate. These vital signs will be obtained at Screening and at End of Treatment, with the exception of blood pressure which is collected at baseline (after randomization but before the initiation of study CRRT) and at 6 hour intervals during the Treatment Period, as well as at End of Treatment.

6.5 Clinical Laboratory Tests

6.5.1 Laboratory Parameters

Clinical laboratory tests are shown in Appendix 1.

6.5.2 Sample Collection, Storage, and Shipping

Sample collection is detailed in Appendix 1. All laboratory samples will be collected, stored, shipped and processed by local laboratories according to each site's procedures.

6.6 Dispensing Study Drug

Prismocitrate 18 must only be used to treat patients enrolled in the study and randomized to the Prismocitrate Group under the sole supervision of the PI. Study drug will be dispensed, recorded on source documents, and entered into eCRFs by site personnel as authorized by the PI.

6.7 Efficacy Variables

6.7.1 Primary Efficacy Endpoint

The Prismaflex M150 Set extracorporeal circuit life will be assessed as a time-to-event endpoint over a maximum 120 hours by the duration of time for which each Prismaflex M150 Set can be used continuously over a maximum 72 hour period in each patient. The Prismaflex M150 Set will be replaced any time CRRT is stopped during the Treatment Period (regardless of duration) or any time a circuit is used for 72 continuous hours (ie, "Advisory Time to Change Set"). The end of the extracorporeal circuit life will be defined by the occurrence of one or both of the following Prismaflex System alarms/conditions if the alarm cannot be mitigated. At this point, study CRRT will be terminated and the extracorporeal circuit replaced because mitigation of the following alarms is not possible:

- "Warning: Filter Clotted", and/or
- "Advisory TMP Too High"

Note: The nurse at the clinical site will document the alarm and rationale to stop treatment on the eCRF. In addition, the Prismaflex logging information from the data cards (one card per patient) will be collected on an ongoing basis and anonymized data will be sent to Baxter for technical analysis. An Independent Adjudicator will make the final determination of the alarm cause by examining the applicable historical electronic data available surrounding the alarm events (see Section 9.9 Primary Endpoint Adjudication).

The extracorporeal circuit life will be censored for cases where the Prismaflex M150 Set has been replaced for reasons other than reaching the end of the extracorporeal circuit life. Only filters for which the end of the extracorporeal circuit life was reached (ie, one or both Prismaflex System alarms/conditions occurred as defined above and alarm causes have been confirmed by an Independent Adjudicator) will be considered 'events' in terms of the statistical analysis.

6.7.2 Secondary Efficacy Endpoints

Systemic and post-filter blood iCa concentrations will be assessed at baseline (systemic only), initiation (systemic only), 1 hour and every 6 hours during the 120 hour Treatment Period and at 120 hours or end of the Treatment Period from the initiation of study CRRT in each patient as indications of both the extent of calcium chelation prior to the CRRT filter and calcium restoration after the CRRT filter. Post-filter iCa will only be measured in the Prismocitrate 18 arm.

Delivery of the prescribed CRRT dose will be based on the patient's weight and daily recordings of the effluent volume (in mL). These data will be used to calculate delivered dose (mL/kg/hour).

6.8 Safety Assessments

Safety endpoints include:

1. Serum bicarbonate and pH will be measured at baseline, initiation and every 6 hours during the 120 hour Treatment Period and at 120 hours or end of the Treatment Period.

- 2. Blood total calcium concentrations will be measured at baseline, initiation, 1 hour and every 6 hours during the 120 hour Treatment Period and at 120 hours or end of the Treatment Period from the initiation of study CRRT.
- 3. Serum electrolytes (sodium, potassium, chloride, phosphate, magnesium, and anion gap) and base excess will be measured at baseline, initiation and every 6 hours during the 120 hour Treatment Period and at 120 hours or end of Treatment Period
- 4. As indicators of citrate accumulation (along with pH), the total calcium/iCa ratio (both measurements in mmol/L) will be measured at baseline, initiation, 1 hour and every 6 hours during the 120 hour Treatment Period and at 120 hours or end of Treatment Period, anion gap and base excess will be measured at baseline, initiation and every 6 hours during the 120 hour Treatment Period and at 120 hours or end of Treatment Period.
- 5. The number, location and duration of bleeding events during the 120 hour Treatment Period will be collected. If a blood transfusion is needed during the 120 hour Treatment Period, the number and type of transfusions along with the number of units infused will be collected.
- 6. Change from baseline to final measurement in laboratory and vital signs measurements will be collected.
- 7. The incidence of adverse events and serious adverse events from the time the patient signs the informed consent form (ICF) until the end of the study will be collected.

6.9 Analysis of Training on Administration of Prismocitrate 18

The end users who need to be assessed prior to use of Prismocitrate 18 in the clinical trial setting (as delegated by an investigator) will be comprised of physicians, nurses, and other clinicians who may be part of prescribing, initiating, or modifying treatment during the 120 hour Treatment Period. The assessment materials,

1407-004 Protocol Training Assessment 2015May26, are provided separate from the protocol through a secure access internet site. Additional assessment materials for specific end user groups may be provided as needed or as determined by an investigator. A descriptive summary of training results on administration of Prismocitrate 18 will be provided in the Clinical Study Report following completion of the study.

6.10 Adverse Events Assessments

An AE is any untoward medical occurrence in a patient or clinical investigational patient administered a study product, and that does not necessarily have a causal relationship with the treatment or drug. An AE can therefore be any unfavorable and unintended sign (including an abnormal laboratory function), symptom (eg, rash, pain, discomfort, fever, dizziness, etc.), organ dysfunction (eg, cardiovascular failure, pancreatitis, etc.), systemic illness (eg, sepsis), or outcome of death temporally associated with the use of the study product, whether or not the event is considered associated with the study product.

- Laboratory and vital sign abnormalities qualify as AEs if medical intervention is required to treat or address the abnormality, if the patient must be discontinued from the study due to the abnormality, or if the value exceeds specific limits defined by the standard-of-care as qualifying it as an AE.
- An elective procedure/surgery that occurs during the course of a study, but is being performed for a documented pre-existing condition and was pre-planned prior to study entry will not qualify as an AE. If, however, the pre-existing condition unexpectedly deteriorates during the study requiring the procedure/surgery to be performed earlier than planned, the condition for which the procedure/surgery is being performed will qualify as an AE.

Adverse events will be collected starting from the time the patient signs the ICF until 30-days post study treatment period (end of the study). During the course of the study, the Investigator or designee shall monitor each patient for the occurrence of any AE. If an AE occurs, a full description of the event should be recorded including the date of onset, severity, time course, description, actions taken, and causal relationship of the AE to the study product(s). Investigators should review and reference the Causality definitions located in Section 6.10.1 when determining the relationship of the AE to the study product. The investigators may also discuss the event(s) with the Baxter Medical Monitor, but the Investigator must make, document and report the relationship for every AE. All AEs must be documented in source documents and on the eCRFs, no matter how common they are for a particular patient and regardless of the causality assigned by the Investigator.

All AEs and SAEs, regardless of relatedness, should be actively solicited and recorded by the Investigator or designee throughout the course of the study. Additionally, any AE voluntarily reported by the patient should be recorded and verified by the Investigator or

designee on the appropriate source documents and eCRF pages. Each SAE will be documented on a separate SAE report form.

The outcome/resolution of all AEs and SAEs will be determined by the Investigator and documented on the AE eCRF and the SAE report form. Investigators will be instructed to follow all AEs/SAEs as follows: Unrelated AEs will be followed until resolution or until the end of the study whichever occurs first. Adverse drug effects (related AEs) and all SAEs (related or not) will be followed until resolution or stable, including following the patient after the end of the study if necessary. The outcome categories that can be chosen on the eCRF by the Investigator include: Fatal, Not recovered/Not resolved (this outcome is reached for AEs which are ongoing when the patient's end of study is due to death related to another AE), Recovering/Resolving (this outcome is reached for AEs which are ongoing at the patient's end of study), Recovered/Resolved with Sequelae (if there are some residual effects caused by the event), Recovered/Resolved, and Unknown.

All SAEs regardless of their relationship to the study product will be submitted to Baxter by the Investigator or designee within 24 hours of becoming aware of the event.

An AE can result from the use of the study product in accordance with the protocol, as well as from an accidental or intentional misuse of the study product or any other treatment error such as unintentional administration or use of another product during the course of the study.

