6.11 Site Reporting Requirements

During the course of the study, the Investigator or designee will routinely monitor each patient for the occurrence of any AE/ADE. If an AE/ADE occurs, the Investigator or designee will complete the AE eCRF which includes the following:

- a. Description of the event
- b. Start and stop date of the event
- c. Timing of the event
- d. Seriousness of the event (yes, no)
- e. Severity of the event (mild, moderate, or severe)
- f. Causality of the event (related to treatment and/or related to the IP)
- g. Outcome of the event (fatal, not recovered/not resolved, recovering/resolving, recovered/resolved with sequelae, recovered/resolved, and unknown)

All SAEs must be reported to the Baxter Global Patient Safety (GPS) within 24 hours of the Investigator or designee becoming aware of its occurrence. The initial 24-hour reporting requirement can be met by using either the electronic SAE eCRF or the paper SAE form. The informed site team member should also contact their site monitor by phone or email to notify him/her of the event. This requirement is irrespective of whether the AE is thought to be possibly related to the study product or not. After the initial 24-

hour reporting, both the Baxter electronic SAE eCRF and the paper SAE report form must be completed for all SAEs. The paper SAE report form is to include copies of documents (de-identified) requested within the form (if applicable). The paper SAE forms should be sent by email to:

In case this email is down, the site must notify GPS by fax: Once received, the SAE report will be reviewed for completeness and forwarded on to the Medical Monitor and Baxter Global Patient Safety within 1 calendar day of receipt.

Follow-up or new information about a SAE should be provided by the investigator/designee using the paper SAE form within 24 hours of becoming aware of the new information. If the follow-up or new information impacts any of the fields in the electronic SAE eCRF the SAE eCRF should be updated within 24 hours of becoming aware of the new information.

If the Investigator suspects the SAE could possibly be a SUSAR, the following should also be contacted as soon as possible:

:
, MD
Baxter Healthcare Corporation
[name]
Tel:
Email:
Other Contacts: , MS
Baxter Healthcare Corporation
Mobile:
Email:
, BSN, RN

Baxter Healthcare Corporation
[name]
Tel: _____ / Mobile: _____
Email:

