Listing 16.2.7.1	Adverse Events Reported Between Signing the ICF and First Study Treatment
Listing 16.2.7.2	Adverse Events (Serious and Non-Serious)
Listing 16.2.7.3	Serious Adverse Events
Listing 16.2.7.4	Complications Related to Blood Loss: Bleeding Events
Listing 16.2.7.5	Complications Related to Blood Loss: Transfusions
Listing 16.2.7.6	Deaths

Listing Number Listing Name Adverse Events (Serious and Non-Serious) Outcome Listing 16.2.7.7 Listing 16.2.7.8 Adverse Events Related to Baxter Device/Product Systemic and Post-Filter Blood Ionized Calcium Concentrations (iCa²⁺) and Listing 16.2.8.1 Corresponding Changes from Baseline Serum Bicarbonate, pH (ABG) and Base Excess and Corresponding Listing 16.2.8.2 Changes from Baseline Blood Total Calcium Concentrations and Total Calcium/Ionized Calcium Listing 16.2.8.3 Ratio and Corresponding Changes from Baseline Serum Electrolytes and Anion Gap and Corresponding Changes from Listing 16.2.8.4 Baseline Creatinine and Blood Urea Nitrogen and Corresponding Changes from Listing 16.2.8.5 Baseline Listing 16.2.8.6 Bleeding Parameters and Corresponding Changes from Baseline Listing 16.2.8.7 Liver Function Tests and Corresponding Changes from Baseline Listing 16.2.9.1 Vital Signs and Corresponding Changes from Screening/Baseline Listing 16.2.9.2 End of Treatment Compliance Initial Treatment Prescription and Changes During Evaluation Period Listing 16.2.9.3 Listing 16.2.9.4 Dialysate Used During Evaluation Period Listing 16.2.9.5 Replacement Solution Used During Evaluation Period Listing 16.2.9.6 Priming Solution Used During Evaluation Period Listing 16.2.9.7 Calcium Gluconate or Calcium Chloride Used During Evaluation Period Listing 16.2.9.8 **CRRT** Treatment Information Listing 16.2.9.9 Prismaflex M150 Set Information Listing 16.2.9.10 **Blood Access Information** Listing 16.2.9.11 **CRRT** Machine and Treatment Modality Listing 16.2.9.12 Prismaflex M150 Set Independent Adjudication Results Listing 16.2.9.13 **Blood Sampling Schedule Compliance** Listing 16.2.9.14 Pre-Blood Pump Solution Used During Evaluation Period Listing 16.2.9.15 Citrate and CRRT Clinical Cases Training/Assessment Questions

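### Protocol 6.10 defines two adverse event outcome codes by how the patient's study ended, so the outcome field cannot separate improving from non-improving ongoing events

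*Protocol*

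**What the plan says.** Protocol 6.10 makes the investigator responsible for the outcome: "The outcome/resolution of all AEs and SAEs will be determined by the Investigator and documented on the AE eCRF and the SAE report form". It offers six categories and explains some of them in brackets. Two of those explanations matter here:

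- *Recovering/Resolving*: "Recovering/Resolving (this outcome is reached for AEs which are ongoing at the patient's end of study".
- *Not recovered/Not resolved*: "AEs which are ongoing when the patient's end of study is due to death related to another AE".

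The same section sets two follow-up rules. For unrelated events, "Unrelated AEs will be followed until resolution or until the end of the study whichever occurs first". Related AEs and all SAEs, by contrast, "will be followed until resolution or stable, including following the patient after the end of the study if necessary". Protocol 7.6 repeats the extended follow-up for related AEs and SAEs. End of study for AE collection is 30 days after the treatment period.

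Protocol 6.11 lists the same six labels, beginning "Outcome of the event (fatal, not recovered/not resolved, recovering/resolving", without definitions. SAP 14.1 puts outcome among the columns of the AE and SAE data listings. The later SAP list of outputs adds Listing 16.2.7.7, "Adverse Events (Serious and Non-Serious) Outcome".

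**The concern.** An outcome code should describe what happened to the event. These two definitions describe what happened to the patient's participation. A site that follows them records an event that is no better, or is worse, as recovering if the patient is alive at end of study. It records an event that was getting better as not recovered if the patient then dies of something else.

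Evaluating safety is a secondary objective of this Phase III trial, and anyone reading the listings will take the labels at their ordinary meaning. Some investigators may also code by ordinary meaning and others by the bracketed definitions. The field would then mix two meanings that cannot be separated afterwards.

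**Working it through.** No arithmetic applies; the plan states no figure on this point. The check is to apply the two definitions to each kind of ongoing event and compare the resulting code with what the label says.

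One assumption is needed. Death from another AE is also an end of study, so read literally the *Recovering/Resolving* definition covers those patients too. I take the more specific definition to govern when the patient dies of another AE.

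| Event ongoing at end of study | Code under Protocol 6.10 | Does the label fit the course? |
|---|---|---|
| Survivor, event improving | Recovering/Resolving | Yes |
| Survivor, event unchanged or worse | Recovering/Resolving | No, too favourable |
| Died of another AE, event had been improving | Not recovered/Not resolved | No, too unfavourable |
| Died of another AE, event not improving | Not recovered/Not resolved | Yes |

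Within each vital status the code is the same whatever the course. Among these ongoing events, the split between the two codes therefore carries only vital status, which the separate listing of deaths (16.2.7.6) already supplies. Two of the four cells are miscoded, in opposite directions.

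**Could another category absorb the mismatch?** *Recovered/Resolved with Sequelae* is for an event that is over but has left residual effects. *Unknown* does not describe an event whose status has been observed. Neither is defined for an event that is unresolved and not improving.

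**Does another passage correct it?** Protocol 6.11 repeats the labels only. SAP 14.1 repeats that the investigator determines the outcome and names the listing column. Neither document redefines the categories.

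**For which events is the code final?** For unrelated non-serious AEs, follow-up stops at end of study, so the code assigned then stands. Related AEs and all SAEs are followed further, until resolved or stable. For these the status may change, but the text does not say that the eCRF outcome is revised, and an event that becomes stable without resolving still has no category that describes it.

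**Where is the field used?** Only in listings. The AE tables in the later SAP output list (14.3.1.5 to 14.3.1.22) are built on counts, seriousness, severity, relatedness and MedDRA terms. None is a table of outcome.

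**The case against.** The strongest reply is that little depends on this field. That is largely right, and it rules out several stronger readings that a reader might infer.

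- *That the listings would hide unresolved AEs in survivors.* They would not. By the protocol's own definition *Recovering/Resolving* marks an event as ongoing, and stop dates are collected (Protocol 6.11) and listed beside outcome (SAP 14.1). What is lost is the distinction between improving and not improving.
- *That the safety profile, or a comparison of resolution between arms, would be tilted in the product's favour.* No such comparison is planned, the same definitions apply in both arms, and the table above shows errors in both directions.
- *That serious persistent harm is finally coded as improving.* SAEs and related AEs are followed past end of study, so the end-of-study status need not be their last observation.
- *That every ongoing AE in a survivor is bound to be coded as recovering.* The investigator determines the outcome, the definitions do not contain the word only, and eCRF completion guidance outside these documents may say more. How sites would code in practice is not known.

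What survives is narrower. The protocol is the controlling text. Its two definitions contradict their labels, and investigator judgement corrects this only if the investigator departs from the written definition.

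**Conclusion.** The point holds as a defect of definition with limited reach. Coding according to Protocol 6.10 gives an inaccurate outcome for non-improving ongoing AEs in survivors and for improving AEs in patients who die of another AE. The outcome field in the listings then cannot separate the two courses.

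Its size cannot be given as a number, because the documents do not state how many AEs are expected to be ongoing at end of study. Its scope can be stated: one descriptive field, with a clearly final effect on unrelated non-serious AEs and an uncertain one on related AEs and SAEs that stabilise without resolving. AE incidence, seriousness, severity and relatedness tables and the primary and secondary efficacy analyses are untouched, and no bias between arms is built in.

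This rests on reading the bracketed text as the operative definitions, and on no correction existing in eCRF guidance that is not part of these documents. It is worth correcting before database lock, but it does not threaten the trial's conclusions.

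**What to change.** Keep the six categories and change two definitions in Protocol 6.10:

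- *Not recovered/Not resolved*: ongoing without improvement at the last observation, whatever the patient's vital status.
- *Recovering/Resolving*: ongoing and improving at the last observation.

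Carry the same wording into the eCRF completion guidance, and state there whether the outcome code is updated when a related AE or SAE is followed beyond end of study. Protocol 6.11 and Listing 16.2.7.7 can then use the labels unchanged.

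Before lock, query two groups of records: AEs coded *Recovering/Resolving* at end of study, and AEs coded *Not recovered/Not resolved* in patients who died of another AE.

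The cost is a wording change and one data query per affected AE. No visit, eCRF field or analysis changes.

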6.10.1 Definitions of Adverse Event Terms

Study Product:	Depending on the protocol, the term "study product" can mean the IP, the comparator product, or the blinded product.
Date of Onset:	The date that the signs and symptoms of the AE began.
Signs & Symptoms vs Diagnosis:	If a definitive diagnosis has been medically established by the physician caring for the patient or by the Investigator, this diagnosis should then be recorded as the AE. If a definitive diagnosis has not been medically established, the signs and symptoms should then be recorded as the AEs.
Diagnosis vs Complications	If a patient experiences not only a diagnosis, but additionally a complication of the diagnosis (ie, myocardial infarction with congestive heart failure), both the diagnosis and the medical complication should be collected and recorded as separate AEs on separate eCRFs.
Severity:	Severity will be assessed for each AE and defined using the following criteria: Mild – Is a transient discomfort and does not interfere in a significant manner with the patient's normal functioning level. The AE resolves spontaneously or may require minimal therapeutic intervention. Moderate – Produces limited impairment of function and can require therapeutic intervention, but produces no sequelae.

Severe – Results in a marked impairment of function and can lead to temporary inability to resume usual life pattern. The AE produces sequelae requiring (prolonged) therapeutic intervention. Causality: Causality Assessment – A determination is made by the Investigator and sponsor as to whether there is a reasonable possibility that the device or drug is etiologically related to/associated with the AE. Causality assessment includes, for example, assessment of temporal relationships, association (or lack of association) with underlying disease, treatment association (or lack of association), presence (or absence) of a more likely cause, and physiologic plausibility. Categories for causality assessment are "probably associated," "possibly associated," "unlikely associated" and "not associated." Probably Associated: An AE follows a strong temporal relationship to the device or drug, and another etiology is unlikely or significantly less likely. Possibly Associated: An AE follows a reasonable temporal relationship to the device or drug, and an alternative etiology is equally or less likely compared to the potential relationship to the device or drug. Unlikely Associated: An AE has little or no temporal relationship to the device or drug and/or a more likely alternative etiology exists. Not Associated: An AE that is due to underlying or concurrent illness, complications, concurrent treatments or effect of another concurrent drug/therapy and is not associated to the device or drug (ie, does not follow a reasonable temporal relationship to the use of the device or drug nor has a much more likely alternative etiology).

